## 6.3 Study Subjects

### 6.3.1 Subject Disposition

Number of subjects randomized, number of subjects who took at least one dose of study medication, number of randomized subjects completing the study and reasons for discontinuation will be summarized overall and by treatment group. A listing of subject disposition will be provided and will include subject ID, date of informed consent, date of randomization, randomized treatment group, result of the pregnancy test, day of first dose, day of last dose, completion (Yes/No), date of discontinuation and reason for discontinuation. Subject disposition will also be presented with a flow chart.

The number of days between the positive diagnosis for COVID-19 infection and the date of randomization will be summarized overall and by treatment group for the ITT population. The same will be done for the number of days between the first COVID-19 symptoms prior to randomization and the date of randomization. The first COVID-19 symptoms prior to randomization will also be displayed.

### 6.3.2 Protocol Deviations

Protocol deviations, as collected on the Protocol Deviation Form of the eCRF, will be summarized overall and by treatment group for the ITT population. Major protocol deviation will be summarized similarly. A listing will also be provided.

### 6.3.3 Datasets Analyzed

The number of subjects in each datasets will be summarized overall and by treatment group. A listing, including reason for being excluded from a given dataset, will be provided as well.

### 6.3.4 Demographic and Baseline Characteristics

Demographic data (age at informed consent, sex, ethnicity, race) and baseline characteristics such as physical appearance (height weight, waist circumference), medical and surgical history (smoking, diabetes, hypertension, dyslipidemia, myocardial infarction, percutaneous coronary intervention, coronary artery bypass graft surgery, stroke, heart failure, respiratory disease) as well as other past or present clinically significant medical or surgical conditions will be summarized using descriptive statistics, overall and by treatment group for the ITT population.

A listing will be presented for demographic data.

### 6.3.5 Prior and Concomitant Medications

Prior and concomitant medications will be coded with respect to indication and generic name using the WHO Drug dictionary (version C March 2018).

Frequency of use of medications at randomization will be presented for the subjects of the ITT population by therapeutic class and preferred term, overall and for each treatment group.

A medication will be flagged as being ongoing at the time of randomization if:

- Medication start date < randomization date
- AND
- Medication end date  $\geq$  randomization date OR Medication is ongoing

In case of missing or incomplete medication start / end dates, the following rules will be applied:

- If 1) the medication start date is completely missing or 2) only the year is specified and it is the same as the randomization year or 3) only the month/year are specified and they are the same as the randomization month/year, then the medication will be assumed to have started before randomization.
- If 1) the medication end date is completely missing or 2) only the year is specified and it is the same as the randomization year or 3) only the month/year are specified and they are the same as the randomization month/year, then the medication will be assumed to have ended after randomization.
- Otherwise, partial medication start / end dates will be compared to the randomization date and the medication will be classified accordingly.

Frequency of use of prior and concomitant medications will also be presented for the subjects of the ITT population by therapeutic class and preferred term, overall and for each treatment group.

### **6.3.6 Study Medication Administration**

Number and proportion of subjects who received study medication, who took study medication and for whom the blinded was maintained will be provided, overall and by treatment group, for the ITT population. Number and proportion of subjects for whom study medication was prematurely discontinued, along with reason, will be displayed as well, overall and by treatment group.

Information on study medication administration will be listed.

## **6.4 Efficacy Analysis**

All efficacy analyses will be conducted on the ITT population.

### **6.4.1 Primary Analysis**

Number and proportion of patients with fever, cough, shortness of breath or anosmia will be summarized at 3, 7, 10 and 14 days, overall and by treatment group.

The primary analysis will compare the proportions of subjects with these symptoms between the two treatment groups using a generalized linear mixed model (GLMM), more precisely a repeated binary logistic regression model, with terms for treatment group (placebo, hesperidin), time (3, 7, 10 and 14 days) and treatment group x time interaction. Contrasts under this model will allow for the comparisons of the proportions at each time point. The primary analysis will be the comparison between treatment

groups at day 7, although treatment groups will also be compared at the other time points. Odds ratios will be provided at each time point with 95% confidence intervals and p-values.

Data for the primary endpoint will be listed.

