**STUDY DESIGN:** This will be a randomized, double-blind, placebo-controlled study. The study will include subjects from Quebec diagnosed with COVID-19 infections. Following informed consent, 216 subjects meeting all inclusion and no exclusion criteria will be randomized to receive either hesperidin 1000 mg once daily (q.d.) or placebo (1:1 allocation ratio) for 14 days. Investigational drug will be delivered to the patients' homes with an electronic oral thermometer and a symptoms diary. Follow-up phone assessments will occur after 3, 7, 10, and 14 days following randomization for evaluation of COVID-19 symptoms. Electronic Case Report Form (eCRF) will be completed by the research personnel over the phone with the patients. The symptoms diary will be mailed back to the coordinating center at the end of the study in a pre-addressed envelope.

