### **3.3 Screening Evaluations and Randomization**

Screening evaluations will include a review of the patient's medical history and assessment of concomitant medications to determine if the patient qualifies for the study. Patients who meet all inclusion criteria and no exclusion criteria will be randomized to receive the study product or placebo. All patients must be randomized within 2 days of the diagnosis of COVID-19 infection.

Women of childbearing potential must have a negative urine pregnancy test result at the time of randomization in order to qualify. Qualifying patients will be randomized to receive placebo or hesperidin 1000 mg/day administered in a blinded manner. Blinded randomization will be performed through a system of envelopes. 108 patients will be randomized to active treatment and 108 patients will be randomized to placebo for a total of 216 randomized patients.

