**Table 1 Timetable of Visits and Procedures**

Visits	1. Screening / randomization (Phone call)	2. Contact Point (Phone) –no window**	3. Contact Point (Phone) (± 1 day)	4. Contact Point (Phone) (± 3 days)	5. Contact Point (Phone call) (± 3 days)
Days	0	3	7	10	14
Informed consent	X				
Demographics	X				
Medical/Surgical history	X				
Review concomitant medication	X	X	X	X	X
Covid-19 symptoms (including date of onset)	X	X	X	X	X
Review Inclusion/Exclusion criteria	X				
Urinary pregnancy test*	X				
Randomization	X				
Record potential study endpoints and other AEs		X	X	X	X
Study medication dispensing	X				
Study medication compliance		X	X	X	X

\*For women of childbearing potential

\*\* If day 3 occurs on the weekend, contact point will be done on previous Friday or following Monday, whichever is closer to day 3.

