### **4.2 Patient Selection Criteria**

#### **4.2.1 Inclusion Criteria:**

All of these criteria must be met:

- Covid-19 positive by polymerase chain reaction (PCR) testing;
- Participant must be able to evaluate their symptoms and report them in the symptoms' diary;
- Patients must be able to take their oral temperature daily with an electronic thermometer provided to them with study materials;
- Males and females, at least 18 years of age, capable and willing to provide informed consent;
- Female patient is either not of childbearing potential, defined as postmenopausal for at least 1 year or surgically sterile, or is of childbearing potential and practicing at least one method of contraception and preferably two complementary forms of contraception including a barrier method (e.g. male or female condoms, spermicides, sponges, foams, jellies, diaphragm, intrauterine device (IUD)) throughout the study;
- Patient must have received a diagnosis of COVID-19 infection within the last 48 hours and have one or more symptoms;
- Outpatient setting (not currently hospitalized or under immediate consideration for hospitalization);
- Patient must be able and willing to comply with the requirements of this study protocol.

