### **8.3 Data analysis**

#### **8.3.1 Analysis of efficacy outcomes**

Efficacy analysis will be based on the intent-to-treat principle. The primary analysis will compare the proportions of subjects with fever, cough, shortness of breath or anosmia between the two treatment groups using a generalized linear mixed model with terms for treatment group (placebo, hesperidin), time (3, 7, 10 and 14 days) and treatment group x time interaction. The primary analysis will be the comparison between treatment groups at day 7, although treatment groups will also be compared at the other time points. Mean number of COVID-19 symptoms will be compared between treatment groups using a Student t-test or a Wilcoxon rank-sum test according to distribution. If more appropriate, a Poisson regression model will be used. Duration of COVID-19 symptoms will be compared between treatment groups using a log rank test and Kaplan-Meier curves will be presented. Subjects who will still have COVID-19 symptoms at the end of the study will be censored at the day of their last phone contact or videovisit. The analysis of individual COVID-19 symptoms over time will be similar to the analysis of the primary endpoint and will use generalized linear mixed models. Composite of COVID-19-related hospitalization, mechanic ventilation or death will be compared between treatment groups using a chi-square test. All statistical tests will be two-sided and conducted at the 0.05 significance level. Statistical analysis will be done using SAS version 9.4 or higher.

Full details of the statistical analysis will be described in a statistical analysis plan that will be finalized and approved prior to database lock.

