## Instructions

This diary is to be used to collect information on the daily symptoms you experience.

This daily diary has been designed with check boxes **to make it easier for you to fill out every day.**

Please check your symptoms every day for 14 days. There is one page for each week that you will be taking the medication starting with Day 1.

We will ask you for the symptoms when we call at the beginning of the study and on day 3, day 7, day 10 and 14. Please have the diary with you.

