#### 6.2.1 Handling of Missing Data

Subjects will be asked to assess daily the presence (Yes/No) of 13 COVID-19 symptoms for a duration of 14 days. Most efficacy endpoints rely heavily on the assessment of these symptoms so a rule has to be defined in case the symptoms are reported as 'Not Done' or are missing.

At any given day (DAY 1 to DAY 14), if some symptoms among the 13 symptoms are reported as 'Not Done' or are missing, these symptoms will be imputed as the last observation carried forward.

On the other hand, if, at any given day, all symptoms are reported as 'Not Done' or are missing, the following will be done:

- If the subject has died, then all symptoms will be imputed as 'Yes' (and symptom "Fever" as greater than 38°) if that day is prior to date of death.

- Otherwise, the symptoms will not be imputed and the assessment on that day will be considered missing.

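### The primary model leaves out the Day 0 symptoms and onset date; the unadjusted test is valid, but pre-specified adjustment would guard the Day 7 result against chance imbalance and may add power

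*SAP*

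**What the plan says.** SAP 6.4.1 specifies a repeated binary logistic model "with terms for treatment group (placebo, hesperidin), time (3, 7, 10 and 14 days) and treatment group x time interaction". Protocol 8.3.1 agrees, "using a generalized linear mixed model with terms for treatment group (placebo, hesperidin), time (3, 7, 10 and 14 days") plus the interaction. The Day 7 contrast is primary. Because the time levels start at Day 3, Day 0 is neither a covariate nor a repeated level. The symptom-count model in SAP 6.4.2 has the same terms.

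The baseline information is scheduled. Protocol Table 1 and SAP Appendix B mark "Covid-19 symptoms (including date of onset") at the Day 0 call, and the diary instructions tell patients "We will ask you for the symptoms when we call at the beginning of the study". SAP 6.3.1 and Table 1.1.2 use this material only to describe the sample.

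On balance, Protocol 3.3 says "Blinded randomization will be performed through a system of envelopes" and names no stratification factor. On entry, Protocol 4.2.1 requires "Patient must have received a diagnosis of COVID-19 infection within the last 48 hours and have one or more symptoms". Neither the number of the four primary symptoms nor the time since onset is restricted.

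The sample size (SAP 6.1) is built on a 20-point difference in proportions. SAP 6.4.1 tabulates the proportions by arm but gives confidence intervals only for odds ratios.

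**The concern.** A patient who enters with cough, anosmia and shortness of breath is plausibly more likely to be positive on the composite at Day 7 than one who enters with a headache. A patient nine days into the illness is plausibly less likely to be positive than one on day two. If so, the unadjusted comparison carries variation that the trial has already measured and could remove.

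The unadjusted test is not biased, and its error rate holds over repeated trials. The trial will, however, have only one allocation. If the arms differ at entry, the unadjusted Day 7 estimate carries that difference, and an adjustment introduced after the baseline table is seen by arm would look post hoc. Specifying it in advance removes that choice.

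**Working it through.** **The plan's own figure.** Inputs from SAP 6.1: 50% vs 30% at Day 7, two-sided 0.05, 80% power.

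- n per arm = (1.960 + 0.842)² × (0.5×0.5 + 0.3×0.7) / 0.20² = 90.3, so 91. This reproduces.
- 91 / 0.85 = 107.1, so 108 per arm and 216 in total. This reproduces.
- SE of the Day 7 difference at 91 per arm = √(0.46/91) = 0.0711, or 7.1 points.
- Power at 91 per arm: 80.3% (unpooled), 79.1% (pooled), 78.0% (Wald test on the log odds ratio).

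**Power with adjustment.** The documents give no link between baseline and Day 7, so every prognostic strength here is an assumption. Day 7 logistic model, 91 per arm, 10,000 simulated trials per scenario, marginal rates held at 50% and 30%. The four Day 0 symptoms were drawn independently at the low ends of the ranges in the Protocol 1.3 symptom-frequency table (fever 0.44, cough 0.57, shortness of breath 0.31, loss of smell and/or taste 0.54, used for anosmia) or at the midpoints. Days since onset were gamma with mean 4 and SD 2. The covariates are the symptom count and days since onset.

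| OR per symptom | OR per day | Low ends: unadjusted → adjusted | Midpoints: unadjusted → adjusted |
|---|---|---|---|
| 1.0 | 1.00 | 79.0% → 79.1% | 78.6% → 78.9% |
| 1.2 | 0.95 | 79.3% → 79.7% | 78.7% → 79.1% |
| 1.5 | 0.90 | 78.3% → 79.7% | 79.0% → 80.6% |
| 2 | 0.85 | 79.1% → 83.5% | 78.8% → 83.2% |
| 3 | 0.80 | 79.0% → 87.1% | 79.1% → 87.0% |

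Repeat runs with fewer replicates agree to within about a point. At OR 1.5, 2 and 3 the SE of the standardised difference falls from 7.1 to about 7.0, 6.8 and 6.4 points. Null rejection was 4.3–4.8% unadjusted and 4.8–5.4% adjusted, so both are close to nominal; a repeat put the adjusted rate as high as 5.7%.

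**Which covariate.** The chance of at least one primary symptom at the low-end frequencies is 1 − 0.56×0.43×0.69×0.46 = 0.924. A yes/no entry status therefore varies little and adds only 0.2–1.6 points at OR 1.5–3. The count and the onset time carry the information. Leaving fever out of the count costs 0.3–2.2 points.

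**Missing baseline values.** If 10% lack them (low-end frequencies), dropping those patients gives 74.9%, 75.4%, 75.6%, 78.7% and 83.6% power at OR 1, 1.2, 1.5, 2 and 3. Filling with the pooled mean gives 79.2%, 79.8%, 79.7%, 82.9% and 86.5%.

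**Chance imbalance.** Let q be the share with any primary symptom at entry. A 1-SD arm difference in that share is √(2q(1−q)/91). Assume 10% of patients without an entry symptom are positive at Day 7; the rate among those with one must then be (0.50 − 0.10(1−q))/q to give 50% overall.

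| q | 1-SD imbalance | Day 7 rate with vs without | Shift in Day 7 difference | In SE |
|---|---|---|---|---|
| 0.85 | 5.3 points | 57% vs 10% | 2.5 points | 0.35 |
| 0.92 | 4.0 points | 53% vs 10% | 1.7 points | 0.25 |
| 0.95 | 3.2 points | 52% vs 10% | 1.4 points | 0.19 |

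The 10% matters. With 30% instead, at q = 0.92, the other rate is (0.50 − 0.30×0.08)/0.92 = 51.7% and the shift is 4.0 × 0.217 = 0.9 points.

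In a separate simulation with a binary baseline status (70–90% prevalence, OR 3–15), an arm difference of 10 points or more arose in about 12–13%, 8% and 2% of trials at 70%, 80% and 90% prevalence. Among those trials the unadjusted type I error was about 5–13% and the adjusted about 4–6%. These conditional figures are imprecise, especially at 90% prevalence, where only about 100 runs qualify.

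**The case against.** The strongest reply is that nothing here is an error. The sample size reproduces, alpha is controlled, and the two documents agree on the model. The benefit is hypothetical: up to OR 1.5 per symptom the gain is about two points or less, and the larger gains need strong symptom effects paired with an onset effect assumed to grow alongside. The simulations use Day 7 alone, not the planned repeated model, whose convergence with two added covariates and their time interactions was not examined. Adjustment also has a cost. It needs a new fever definition and a missing-data rule, and the annotated case report form that would show whether Day 0 status exists per symptom is not available here. SAP 6.3.1 speaks of first symptoms before randomization, which need not be current status. A pre-specified adjusted sensitivity analysis would leave the primary test alone.

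Much of this stands as a limit on size. The gain may be nil, and the Day 0 data need checking before the covariates are fixed. It does not remove the point. When the covariates were not prognostic, power was essentially unchanged, so little is risked provided no subject is dropped. An adjusted sensitivity analysis would be second best: it would show the effect of an imbalance but leave the headline result exposed to it. The confidence interval for the risk difference is a separate reporting matter, but it belongs here because it answers the complaint that an adjusted odds ratio is conditional.

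**Conclusion.** The concern holds, as lost efficiency and robustness rather than bias. The primary model omits baseline information that the trial schedules at Day 0, and no adjusted analysis is planned. About 80% power and the 5% error rate stand without it. Under assumed prognostic strengths, adjustment adds from nothing to about 8 points of power, with about 4 points at OR 2 per symptom. It also removes a shift of roughly 1.4–2.5 points per 1-SD imbalance in entry status, if 10% of patients without an entry symptom are positive at Day 7.

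These sizes rest on independent symptoms, an assumed onset distribution and a Day 7-only model. The change should be made, but the trial is not invalid without it.

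**What to change.** Amend SAP 6.4.1 before unblinding:

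1. Add two covariates, each with a time interaction: the Day 0 number of the four primary symptoms, and days from first symptom to randomization.
2. Define Day 0 fever from what the Day 0 call records, for example patient-reported fever. The drug is delivered "with an electronic oral thermometer and a symptoms diary", so a reading against the SAP 4.1 threshold of 38° may not exist at Day 0. If fever is not recorded, use the count of the other three symptoms.
3. Fill missing baseline covariates and partial onset dates with the pooled mean, blind to arm, so that no ITT subject is dropped. The rule in SAP 6.2.1 ("At any given day (DAY 1 to DAY 14), if some symptoms among the 13 symptoms are reported as" not done or missing) starts at Day 1 and does not cover baseline.
4. Report the model-standardised Day 7 difference in proportions with a 95% confidence interval beside the odds ratio, and state whether that odds ratio is marginal or subject-specific.
5. Keep the unadjusted model as a sensitivity analysis.

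In SAP 6.4.2, add the baseline symptom count to the symptom-count model.

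The downside is that the adjusted odds ratio becomes conditional on the covariates; item 4 deals with that. The cost is SAP wording and a check that the eCRF holds Day 0 status for each of the four symptoms. No patients or visits are added.

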#### 6.4.2 Secondary Analysis

- Number of COVID-19 symptoms (range 0 – 13) will be summarized using descriptive statistics at 3, 7, 10 and 14 days, overall and by treatment group.

Mean number of COVID-19 symptoms will be compared between treatment groups using a repeated measures analysis of variance (ANOVA) model with terms for treatment group (placebo, hesperidin), time (3, 7, 10 and 14 days) and treatment group x time interaction. Contrasts under this model will allow for the comparisons of the mean number of symptoms at each time point. Mean differences will be presented with 95% confidence intervals and p-values. If more appropriate given the distribution of the data, a Poisson regression model for repeated measures could be used.

- Number and proportion of subjects with complete disappearance of COVID-19 symptoms after randomization will be provided overall and by treatment group. In those subjects, duration of symptoms will be summarized using descriptive statistics.

Duration of COVID-19 symptoms will be compared between treatment groups using a log rank test and Kaplan-Meier curves will be presented.

- Individual COVID-19 symptoms over time (3, 7, 10 and 14 days) will be presented and analyzed as the primary endpoint, using the statistical approach described in section 6.4.1.

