## 2 STUDY DESCRIPTION

### 2.1 Study Design

This will be a randomized, double-blind, placebo-controlled study. The study will include subjects from Quebec diagnosed with COVID-19 infections. Following informed consent, 216 subjects meeting all inclusion and no exclusion criteria will be randomized to receive either hesperidin (1000 mg q.d.) or placebo (1:1 allocation ratio) for 14 days. Investigational drug will be delivered to the patients' homes. In addition, patients will be provided with an oral electronic thermometer as well as a daily symptoms diary (see Appendix A). Follow-up phone assessments will occur after 3, 7, 10, and 14 days following randomization for evaluation of the occurrence of any trial endpoints or other adverse events. Electronic CRF (eCRF) will be completed by the research personnel over the phone with the patients.

The schedule of visits for this study is outlined in Appendix B. However, a patient may be evaluated at any time for safety concerns.

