## 6 STATISTICAL METHODOLOGY

### 6.1 Determination of Sample Size

Sample size is based on the proportion of subjects with any of the following COVID-19 symptoms: fever, cough, shortness of breath or anosmia at day 7 since this time point will be the primary focus. Using a two-sided 0.05 significance level, sample sizes of 91 in both groups (182 total) will achieve 80% power to detect an absolute between groups difference of 20% in the proportion of subjects with the above COVID-19 symptoms at day 7. This is assuming that the proportions of patients with the above COVID-19 symptoms at day 7 will be 50% in the placebo group and 30% in the active treatment group. Factoring in a 15% drop out rate, a total of 216 patients will be randomized in the study (108 per group).

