### 6.2 Statistical Considerations

Baseline, efficacy and safety data will be reported using descriptive statistics. N, mean, standard deviation, median, Q1, Q3, minimum and maximum will be provided for continuous variables. Count and frequency will be provided for categorical variables.

Basic assumptions of the proposed analyses will be verified prior to the analyses. Subject disposition, datasets analyzed, baseline characteristics and efficacy analyses will be carried out on the ITT population defined in Section 3.1 according to the intent to treat principle. Safety analyses will be done on the safety population defined in Section 3.2.

All statistical tests will be two-sided and conducted at the 0.05 significance level. Statistical analyses will be done using SAS version 9.4 or higher.

A fully independent 3-member Data and Safety Monitoring Board (DSMB) will be established and will review unblinded data as detailed in the DSMB charter after randomization of 50, 100 and possibly 150 subjects. The DSMB charter will pre-specify the rules for early study termination, approved by all board members.

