## APPENDIX B TIMETABLE OF VISITS AND PROCEDURES

Visits	1. Screening / randomization (Phone call)	2. Contact Point (Phone) – no window	3. Contact Point (Phone) ( $\pm 1$ day)	4. Contact Point (Phone) ( $\pm 3$ days)	5. Contact Point (Phone call) ( $\pm 3$ days)
Days	0	3	7	10	14
Informed consent	X				
Demographics	X				
Medical/Surgical history	X				
Review concomitant medication	X	X	X	X	X
Covid-19 symptoms (including date of onset)	X	X	X	X	X
Review Inclusion/Exclusion criteria	X				
Urinary pregnancy test*	X				
Randomization	X				
Record potential study endpoints and other AEs		X	X	X	X
Study medication dispensing	X				
Study medication compliance		X	X	X	X

\*For women of childbearing potential

\*\*If day 3 occurs on the weekend, contact point will be done on previous Friday or following Monday, whichever is closer to day 3.

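### The model for the 0–13 symptom count has no Day 0 symptom covariate; adding one is a nearly free gain in precision, of a size the documents do not settle

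*SAP*

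**What the plan says.** SAP 6.4.2 analyses the number of symptoms with a "repeated measures analysis of variance (ANOVA) model with terms for treatment group (placebo, hesperidin), time (3, 7, 10 and 14 days", together with the treatment-by-time interaction. Contrasts at each visit give mean differences with 95% confidence intervals and p-values. A repeated-measures Poisson model is the fallback, and no covariate is named for it. Protocol 8.3.1 proposes a t-test or rank-sum test for the same endpoint, also unadjusted. No efficacy model in either document contains a baseline covariate.

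Symptoms are nevertheless scheduled before treatment. In SAP Appendix B the row "Covid-19 symptoms (including date of onset" is marked in the Day 0 column, and Protocol Table 1 (Timetable of Visits and Procedures) agrees. The diary instructions in Protocol Appendix E tell patients: "We will ask you for the symptoms when we call at the beginning of the study". The SAP's only planned use of pre-randomization symptoms is descriptive (6.3.1 and Table 1.1.2).

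**The concern.** Protocol 4.2.1 asks only for at least one symptom at entry, so patients can start with very different symptom loads. If a patient with many symptoms at Day 0 tends to have more at Day 3 or Day 7, part of the between-patient spread at those visits is predictable from data taken before treatment. A model without the Day 0 value leaves that part in the residual variance. Modelling the correlation among Days 3 to 14 does not recover it, because the Day 0 value is not in the model.

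At stake is the width of the intervals for the first-listed secondary endpoint. The trial was sized only for the binary Day 7 composite, so precision for the count was never planned.

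**Working it through.** **The plan's own figure.** SAP 6.1 states "sample sizes of 91 in both groups (182 total) will achieve 80% power to detect an absolute between groups difference of 20" percentage points, with proportions that "will be 50% in the placebo group and 30% in the active treatment group". SAP 6.2 sets the level: "All statistical tests will be two-sided and conducted at the 0.05 significance level". With unpooled variance:

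n = (1.960 + 0.842)² × (0.5×0.5 + 0.3×0.7) / 0.20² = 7.85 × 0.46 / 0.04 = 90.3, rounded up to 91 per group.

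For dropout, the SAP says "Factoring in a 15% drop out rate, a total of 216 patients will be randomized in the study (108 per group": 91 / 0.85 = 107.1, rounded up to 108 per group, or 216. The figures reproduce. (A pooled-variance formula gives 93 per group, a trivial difference.) They concern the primary endpoint and are not affected by this point. They supply only the 91 evaluable patients per arm used below.

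**Inputs for the count.** Two-sided 0.05, 1:1 allocation and 91 per arm come from the SAP. The SD of the count, a target difference and the correlation r between the Day 0 count and the later count are in neither document. Results are therefore in SD units, over an assumed range of r.

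**Unadjusted precision at one visit.**
- Standard error of the difference: √(2/91) = 0.148 SD.
- 95% half-width: 1.96 × 0.148 = 0.291 SD.
- Difference detectable with 80% power: 2.802 × 0.148 = 0.415 SD.

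**Adjusted precision.** Conditioning on the Day 0 count multiplies the residual variance by 1 − r². The lost degree of freedom and chance imbalance multiply the standard error by about √(179/178) = 1.003. The width ratio is therefore √(1 − r²) × 1.003.

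| Assumed r | Width ratio | Half-width (SD) | Interval narrower by | Equivalent sample-size factor 1/(1 − r²) |
|---|---|---|---|---|
| 0.1 | 0.998 | 0.290 | 0.2% | 1.01 |
| 0.2 | 0.982 | 0.285 | 1.8% | 1.04 |
| 0.3 | 0.957 | 0.278 | 4.3% | 1.10 |
| 0.4 | 0.919 | 0.267 | 8.1% | 1.19 |
| 0.5 | 0.869 | 0.252 | 13% | 1.33 |

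Break-even is at r = √(1 − 178/179) ≈ 0.07. Below that, adjustment gains nothing and costs at most about 0.3% in width. A simulation of 2,000 trials with normal data at 91 per arm gave mean standard-error ratios of 0.956 at r = 0.30 and 0.870 at r = 0.50, in agreement with the table.

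**The same thing as power.** Take a contrast that happens to have 80% power unadjusted. This is a hypothetical starting point, because the plan states no power for the count. Adjusted power is Φ(2.802/√(1 − r²) − 1.960): 83.6% at r = 0.3, 86.4% at 0.4 and 89.9% at 0.5.

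**Is the Day 0 count there?** The timetables and the diary instructions show that symptoms are asked about at the first call. They do not show that all 13 items are recorded. SAP 4.3 and 6.2.1 describe the daily symptom assessments for Days 1 to 14, and the diary grid also starts at Day 1. SAP 4.2 scores fever from a temperature above 38°, but the Protocol Synopsis (Study Design) has the thermometer delivered to the home with the study product, whereas Day 0 is a phone call. Measured fever may therefore be absent at Day 0. A covariate need not match the outcome item for item, so a count of the items that are recorded can still serve.

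**The case against.** The strongest case against has three parts.

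First, nothing in the documents establishes that the outcome itself exists at Day 0. The planned descriptive display in SAP 6.3.1 concerns the first symptoms before randomization, which may be an onset history and not a current 13-item count. A reader might infer from the timetable that the same quantity is available before treatment. The documents do not go that far, and scoring Day 0 by the rule in SAP 4.2 may be impossible for fever. This stands: it decides how the covariate must be defined and makes the point conditional on what the Day 0 eCRF holds.

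Second, the size is assumed throughout. Eligibility limits time since diagnosis, not time since symptom onset, so patients may enter at different stages of illness, which could weaken the correlation. Symptoms also resolve over two weeks. A reader might infer that power is being wasted at all four visits. That is not supported: the correlation could be near zero by Day 10 or Day 14. This also stands, and is why only a range is given.

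Third, the planned analysis is not wrong. Randomization makes the unadjusted contrast unbiased, and its interval already allows for chance imbalance at entry. The plan is consistent in adjusting nothing, and this is a secondary endpoint with no power claim. All of that is correct. It sets the weight of the point but does not remove it, because adjustment costs almost nothing even where it gains nothing.

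**Conclusion.** The point holds as a free improvement in precision, not as an error. SAP 6.4.2 leaves out a baseline symptom covariate that the visit schedule appears to make available, and gives no reason. On an assumed within-arm correlation, the 95% interval for the mean difference would be about 4% narrower at r = 0.3 and 13% narrower at r = 0.5, and practically unchanged near r = 0.1. The gain is probably largest at Day 3 and smallest at Day 14.

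This rests on three assumptions: that the Day 0 eCRF holds a usable set of current symptoms, that r lies in the range shown, and that about 91 patients per arm contribute. The arithmetic is for the linear model and was not repeated for the Poisson alternative.

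A reader might go further and conclude that the reported differences will be biased, or the tests invalid, because entry symptom burden is ignored. The documents do not support that. With "placebo (1:1 allocation ratio) for 14 days" assigned at random, only precision is affected.

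**What to change.** Before unblinding, amend SAP 6.4.2 as follows.

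- Add to the repeated-measures model the number of COVID-19 symptoms recorded as present on the Day 0 eCRF, and its interaction with time. Report the baseline-adjusted mean differences with 95% confidence intervals at Days 3, 7, 10 and 14.
- Define the Day 0 count from the items available at Day 0. Where no temperature was measured, use reported fever or feverishness and do not apply the temperature rule of SAP 4.2.
- In the Poisson alternative, enter log(Day 0 count + 1).
- Replace a missing Day 0 count with the overall mean of the Day 0 counts, so that no patient is dropped.

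The cost is a few sentences of SAP text, a short definition of the Day 0 count and one degree of freedom per time point. No new data, visits or patients are needed. The Day 0 eCRF form, which is not among the documents, should be checked first to confirm which items it records. The covariate should be fixed before treatment codes are known, because choosing it afterwards would invite criticism.
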